8.4. Exclusion Criteria

A subject who meets any of the following criteria will be excluded from participation in this study.

- 1. Subject has untreated Addison's disease, thyroid disorder, growth hormone deficiency, hypopituitarism or definite gastroparesis, per investigator judgment.
- 2. Subject is using pramlintide, DPP-4 inhibitor, GLP-1 agonists/mimetics, metformin, SGLT2 inhibitors at time of screening.
- 3. Subject has had renal failure defined by creatinine clearance <30 ml/min, as assessed by local lab test \leq 12 months before screening or performed at screening at local lab, as defined by the creatinine-based Cockcroft or MDRD equations.
- 4. Subject is planning to switch from FGM to CGM therapy during the 6 months study phase.
Note: Subject randomized to Control Arm should remain on their current FGM or CGM therapy during the study phase and will be switched to AHCL during the continuation phase.
- 5. Subject has a history of hearing or vision impairment hindering perception of glucose display and alarms, or otherwise incapable of using the study devices, per investigator judgment.
- 6. Women of child-bearing potential who have a positive pregnancy test at screening or plan to become pregnant during the course of the study.
- 7. Females who are sexually active and able to conceive will be excluded if they are not using an effective method of contraception and do not agree to continue using an effective method of contraception for the duration of the study, per investigator judgment.
- 8. Subject has any unresolved adverse skin conditions in the area of sensor placement (e.g. psoriasis, dermatitis herpetiformis, rash, Staphylococcus infection).
- 9. Subject is actively participating in an investigational study (drug or device) wherein he/she has received treatment from an investigational study drug or device in the last 2 weeks before enrollment into this study, as per investigator judgment.
- 10. Subject is currently abusing illicit drugs, marijuana, alcohol or prescription drugs (other than nicotine), per investigator judgment.

11. Subject has any other disease or condition that may preclude the patient from participating in the study, per investigator judgment.
12. Subject is legally incompetent, illiterate or vulnerable person.
13. Research staff involved with the study.

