8.3. Inclusion Criteria

Subjects will be considered included in the study, if they meet all the following criteria and none of the exclusion criteria:

1. Subject is age ≥ 18 years old at time of screening
2. Subject has a clinical diagnosis of Type 1 diabetes for ≥ 2 years prior to screening as determined via source documentation
3. On MDI therapy (defined as ≥ 3 insulin injections per day and/or a basal/bolus regimen) ≥ 2 years prior to screening
4. Subject has been followed and treated by the investigator at this investigational site for at least 3 months prior to screening and subject has already undergone local educational therapeutic programs.
5. Subject is using:
 - Flash Glucose Monitoring (FGM) for ≥ 3 months with a daily average number of scans ≥ 5 over and with sensor readings $> 70\%$ of time over the previous month prior to screening (based on sensor usage from the download summary report of the FGM system over 30 days prior to screening)

Or

- Continuous Glucose Monitoring (CGM) for \geq 3 months with a frequency of sensor use \geq 70% of the time over the previous month prior to screening (based on download summary report from the CGM system over 30 days prior to screening).
- 6. Subject has a glycosylated hemoglobin (HbA1c) \geq 8.0% (64 mmol/mol) at time of screening visit (as processed by a Central Lab).
- 7. Subject is willing to take or switch to one of the following insulins:
 - a. Humalog™* (insulin lispro injection)
 - b. NovoLog™* (insulin aspart)
- 8. Subject must have a minimum daily insulin requirement (Total Daily Dose) of \geq 8 units and a maximum of 250 units.
- 9. Subject is willing to upload data from the study pump and meter, must have Internet access and a compatible computer system that meets the requirements for uploading the study pump data at home.
- 10. Subject is willing and able to sign and date informed consent, comply with all study procedures and wear all study devices, as required during the study.

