9.2. STUDY START and RUN-IN PHASE

Visit 1: Screening

At this visit, the subject will come at the site or the visit will be conducted remotely:

Medtronic Business Restricted

The Investigational site staff will:

- Determine if subject meets eligibility criteria (see sections 8.3 and 8.4).
- Collect demographic information (age, gender)
- Review subject's Medical History: including date of Type 1 DM diagnosis, indication for Glucose Monitoring System, diabetes-related complications, length of time on MDI therapy (inclusion criteria ≥ 2 years), mean daily insulin dose, insulin molecule, type of FGM or RT-CGM therapy (model) with average number of scans and percentage of sensor readings for FGM users over the previous month (based on downloaded report) or percentage of use of CGM over the previous month (based on downloaded report) for CGM users (*Download Reports will be printed, signed and filed in the source document of the subject*).
- Measure/Collect height and weight
- Perform blood sample collection for **HbA1c** with central laboratory kit.
 - *Reminder: HbA1c value $\geq 8.0\%$ (64 mmol/mol) for inclusion*
Screening status will be confirmed once HbA1c result is received by the site from central lab. Repeated testing will not be permitted. Lab result will be printed, signed and filed in the source document of the subject.

If the Visit 1 is conducted remotely, a nurse will visit the subject to collect the blood sample.

- Perform blood sample collection for **creatinine clearance** at local lab, if needed.
 - If creatinine clearance test was performed ≤ 12 months prior to screening, only confirm date of collection at local lab and creatinine clearance value in medical chart.
Reminder: creatinine clearance threshold for exclusion < 30 mL/min and must be calculated with the Cockcroft or MDRD equations. The sites will follow routine practice for evaluation of the creatinine clearance. If the visit 1 is conducted remotely, a nurse visit can be organized with the subject to collect the blood sample.
- Perform **pregnancy test** at local lab (urinary or blood test), if applicable. The blood or urine sample will be collected and disposed according to the local Lab procedure.
If the Visit 1 is conducted remotely, a nurse will visit the subject to collect the blood sample.
Alternatively, a urinary pregnancy test can be shipped to the subject, if applicable. Result will be documented in medical chart.
- Report any Adverse Events, if applicable

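### Exclusion criterion 7 joins its two contraception conditions with 'and', so a woman who uses contraception at screening but declines to continue it is not excluded

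*Protocol*

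**What the plan says.** Protocol section 8.4 opens with the rule that "A subject who meets any of the following criteria will be excluded from participation in this study". Each numbered criterion therefore acts alone, and what matters is the logic inside each one.

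Criterion 7 has three parts. The population: "Females who are sexually active and able to conceive will be excluded". The two conditions: "if they are not using an effective method of contraception and do not agree to continue using an effective method of contraception". The period and qualifier: "for the duration of the study, per investigator judgment". The synopsis carries the same criterion with the same connector. The SAP (section 5.2) refers to the inclusion and exclusion criteria without restating them, so it gives no alternative wording.

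The neighbouring criterion 6 excludes "Women of child-bearing potential who have a positive pregnancy test at screening or plan to become pregnant during the course of the study". Under Visit 1 in section 9.2, site staff are told: "Perform pregnancy test at local lab (urinary or blood test), if applicable". Table 5 marks that test as optional at Visit 1 and at no other visit, and Table 6 has no row for it.

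**The concern.** The part of criterion 7 about continuing contraception can only matter for someone who already uses it. For that woman the first condition (not using) is false, so the joint condition is false whatever she says about continuing. The clause is inoperative for the one group it naturally addresses.

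This looks like a common drafting slip. A requirement to use contraception and to keep using it was turned into an exclusion by negating each half, and the 'and' was left in place. Criterion 6, one line earlier, uses 'or' where either fact alone excludes, so a careful reader has reason to take the different connector in criterion 7 as deliberate.

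At stake is an eligibility safeguard meant to last for about 13 months of participation (section 6). Section 9.13 prohibits waivers from the plan, apart from a short list of situations that are not deviations. Section 9.13.2 lists enrolment of a subject who fails the criteria among the deviations that could affect safety or data integrity. On the present text, enrolling a woman who declines to continue contraception is not such a deviation, so a monitor has no wording to rely on in raising it.

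**Working it through.** The plan gives no figure here to reproduce. The check is a truth table, followed by a search of the protocol for text that closes the gap.

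**Inputs.** For a woman in the population named in criterion 7, let U = uses effective contraception at screening, and A = agrees to effective contraception for the duration of the study. Both come from section 8.4, criterion 7.

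**Rules compared.**
- As written: exclude if (not U) and (not A).
- With 'or': exclude if (not U) or (not A).
- Agreement only: exclude if (not A).

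| U | A | As written | With 'or' | Agreement only |
|---|---|---|---|---|
| yes | yes | eligible | eligible | eligible |
| yes | no | **eligible** | excluded | excluded |
| no | yes | eligible | excluded | eligible |
| no | no | excluded | excluded | excluded |
| Combinations excluded | | 1 of 4 | 3 of 4 | 2 of 4 |

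These count logical combinations, not shares of subjects. The second row is the gap. Both alternative rules close it, and they differ only in the third row.

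**Does another provision catch the second row?**
- Criterion 6 catches her only if she tests positive at screening or plans a pregnancy. A woman who declines to continue but has no such plan passes.
- Criterion 11 reads "Subject has any other disease or condition that may preclude the patient from participating in the study, per investigator judgment". Declining contraception is neither a disease nor, in any ordinary reading, a condition of that kind.
- Inclusion criterion 10 asks that a subject be willing and able to "comply with all study procedures and wear all study devices, as required during the study". No listed procedure requires contraception.
- The randomization criteria (section 8.5) concern sensor wear, sensor tolerance, fingerstick frequency and compliance with procedures.
- The withdrawal section (9.14) does not mention pregnancy or contraception.
- The only scheduled pregnancy test comes before all of this, at Visit 1.

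**How long after that test does exposure to the investigational pump begin in the control arm?** By target intervals, Visit 9 falls at 7 days (Visit 2) + 14 days (Visit 4) + 7 days (Visit 5) + 3 months (Visit 7A) + 3 months (Visit 8) + 14 days (Visit 9). That is 6 months plus 42 days, or about 7 months after Visit 1. Over that interval the screening criterion is the only protocol-level provision dealing with contraception.

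**The case against.** The best case on the other side has four parts.

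First, sites may read the sentence sensibly. Continuing presupposes current use, and the criterion ends with investigator judgment, so many investigators will probably require both use and agreement. That makes literal application less likely. It does not change the connector, though, and it allows sites to differ.

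Second, criterion 6 removes the most obvious reason for declining, a planned pregnancy. This stands, and it narrows the gap to women who decline without such a plan.

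Third, a reader might infer that the plan means to exclude three of the four combinations and so wrongly admits two. The documents do not support that. No section states such an intent. The duration clause says how long contraception must last, not that use at screening is a separate requirement. A woman who uses none at screening but agrees to use it may have been left eligible on purpose.

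Fourth, a reader might infer that every woman admitted through the gap is a safety exposure with a compromised HbA1c measurement. Declining to continue contraception is not a pregnancy, and neither document says how pregnancy would affect HbA1c or glycaemic targets. That inference should not be drawn from this material. Likewise, the single Visit 1 test and the late pump start in the control arm show that nothing else fills the gap. They are not in themselves defects that rewording criterion 7 would cure.

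**Conclusion.** The point holds for one combination: current use without agreement to continue, and with no planned pregnancy. For that woman the written criterion gives a result at odds with its own duration clause, in both places where it appears, and no other criterion or scheduled procedure corrects it.

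The practical size is small. Few subjects are likely to be affected, and sample size, alpha, power and the primary analysis are untouched. It is worth correcting because it is a safety-related eligibility rule and the correction costs almost nothing.

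The conclusion rests on the literal wording and on the protocol and SAP alone. The consent form, case report form, visit procedures table and worksheets are held separately (sections 15.4.1.2, 17.3, 17.4 and 17.8). Whether any of them contains a contraception undertaking, or records the two answers separately, cannot be judged here.

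**What to change.** Reword criterion 7 in section 8.4 and in the synopsis so that not agreeing to effective contraception for the duration of the study is enough on its own to exclude.

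The sponsor should state explicitly whether a woman who uses no contraception at screening but agrees to use it is eligible, because the answer decides the wording. If she is not eligible, replacing 'and' with 'or' is sufficient. If she is, the criterion should rest on the agreement alone, phrased as agreeing to use rather than to continue using. This review takes no position on which of the two is right.

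The sponsor should also check that the separately held consent and data-collection documents follow the same logic.

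The cost is a short text change in two places, which can go into the next amendment. The downside is that a very small number of women eligible on the present literal wording would be excluded. No statistical section needs to change.

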8.5. Randomization Criteria

If subjects meet the above criteria, as well as all the following criteria assessed at the end of the run-in period, they may continue to participate in the study phase:

1. Subject has worn the sensor with blinded transmitter during the run-in period adequately, per investigator judgment.
2. Subject has shown acceptable tolerance to sensor wear, per investigator judgment.
3. CareLink data shows subject performed ≥ 2 finger stick blood glucose measurements daily, as determined by CareLink data upload as the mean number of SMBG/day over the past 14 days.
4. Subject has shown compliance with study procedures, per investigator judgment.

9. Study Procedures

The below section and appendix 17.8: CIP327 Study Visit Procedures Table describe the study procedures that the subject will undergo during the clinical study.

[figure not shown]
9.1. Schedule of Events

Under pandemic situation, all the visits can be conducted remotely (via phone or video call) and organized accordingly (see details below), per Investigator decision. Investigator may decide to conduct a remote visit during pandemic to maintain safety and when onsite visit is not possible as it would expose subject and staff to increased risks. Rationale will be documented in the source files.

CIP327 (ADAPT) Clinical Investigation Plan

Figure 8: Visit schedule overview

^x Visits allowed to be conducted remotely in pandemic period.

The ADAPT study is comprised of a run-in phase of approximately 2 weeks, a study phase of 6 months and a continuation phase of 6 months.

Prior to study start, Investigator or authorized designee must obtain written informed consent from the patient before any clinical study related activity (including screening) takes place and document informed consent process in the medical chart of the patient (refer to section 9.9 Subject Consent).

Eligible subjects must successfully complete the run-in phase by demonstrating tolerance to sensor wear and compliance with blinded Continuous Glucose Monitoring (CGM) prior to being randomized for the study phase, in which subjects will either be using the AHCL (Treatment Arm = T) or will continue under their MDI therapy + FGM/CGM (Control Arm = C) for another 6 months. After the end of the study phase of 6 months, subjects randomized to the Control Arm will crossover to AHCL pump therapy for another 6 months starting with an AHCL training program.

Successful completion of run-in phase requires blinded sensor glucose data and an average of at least 2 blood glucose (BG) measurements per day during the run-in phase. If this is not achieved (e.g. sensor felt off) the run-in phase can be extended for another 7 to 14 days to repeat Blinded CGM.

Subjects that are randomized to the Treatment arm (T) will start a AHCL training program, including e.g. infusion set insertions/replacements, meal bolus procedure, what to do when exercising, when to perform calibrations, what to do with significant illness, how to react on safety/alert notifications, when to perform BG measurements and when to contact site staff and/or the HelpLine with the contact information provided.

Study Staff will conduct remote (via phone or video) or onsite visit following the Study Visit Schedule (Figure 8). The recommended minimum time on pump therapy alone before starting CGM in Manual Mode, and thereafter CGM in Auto Mode, is 7 days. Subjects will stop FGM/CGM at visit 6A, when starting on CGM in Manual Mode with AHCL system. Study staff will conduct at the minimum a subject visit (or may substitute for a phone contact) 3 days after pump, Manual Mode and Auto Mode have been started. Additional phone contacts or visits may be conducted (unscheduled visits), as needed.

Subjects will be expected to use Auto Mode at all times at home after completion of the pump training, and to perform approximately monthly uploads of the system, with a minimum upload prior to each phone or site contact for therapy review by site staff.

After the end of the study phase of 6 months, subjects randomized to the Control Arm will crossover to AHCL pump therapy for another 6 months starting with an AHCL training program.

Study staff will discuss with the participant the visit schedule and will make arrangements with the subjects for the contacts at site and the 24hr HelpLine (if applicable). Participants who are not compliant with the arranged contacts, which may impact patient's safety, may be discontinued at the discretion of the investigator.

9.2. STUDY START and RUN-IN PHASE

Visit 1: Screening

At this visit, the subject will come at the site or the visit will be conducted remotely:

Medtronic Business Restricted

The Investigational site staff will:

- Determine if subject meets eligibility criteria (see sections 8.3 and 8.4).
- Collect demographic information (age, gender)
- Review subject's Medical History: including date of Type 1 DM diagnosis, indication for Glucose Monitoring System, diabetes-related complications, length of time on MDI therapy (inclusion criteria ≥ 2 years), mean daily insulin dose, insulin molecule, type of FGM or RT-CGM therapy (model) with average number of scans and percentage of sensor readings for FGM users over the previous month (based on downloaded report) or percentage of use of CGM over the previous month (based on downloaded report) for CGM users (*Download Reports will be printed, signed and filed in the source document of the subject*).
- Measure/Collect height and weight
- Perform blood sample collection for **HbA1c** with central laboratory kit.
 - *Reminder: HbA1c value $\geq 8.0\%$ (64 mmol/mol) for inclusion*
Screening status will be confirmed once HbA1c result is received by the site from central lab. Repeated testing will not be permitted. Lab result will be printed, signed and filed in the source document of the subject.

If the Visit 1 is conducted remotely, a nurse will visit the subject to collect the blood sample.

- Perform blood sample collection for **creatinine clearance** at local lab, if needed.
 - If creatinine clearance test was performed ≤ 12 months prior to screening, only confirm date of collection at local lab and creatinine clearance value in medical chart.
Reminder: creatinine clearance threshold for exclusion < 30 mL/min and must be calculated with the Cockcroft or MDRD equations. The sites will follow routine practice for evaluation of the creatinine clearance. If the visit 1 is conducted remotely, a nurse visit can be organized with the subject to collect the blood sample.
- Perform **pregnancy test** at local lab (urinary or blood test), if applicable. The blood or urine sample will be collected and disposed according to the local Lab procedure.
If the Visit 1 is conducted remotely, a nurse will visit the subject to collect the blood sample.
Alternatively, a urinary pregnancy test can be shipped to the subject, if applicable. Result will be documented in medical chart.
- Report any Adverse Events, if applicable

If Visit 2 is planned to be conducted remotely, site staff can start initial training of the subject on Blinded CGM usage (sensor insertion, transmitter use) at this visit.

Visit 2: Start Run-In [Visit 1 +7 days (Window min + 3 d / max + 14 d)]

This visit can be done remotely or onsite.

- Site staff should confirm HbA1c result has been received prior to the visit and meet inclusion criteria (HbA1c $\geq 8.0\%$, 64 mmol/mol).

Once eligibility has been confirmed, subject will start a 2-week run-in phase.

The objective of the 2-week run-in phase is to collect baseline data of CGM and assess subjects' compliance and ability to comprehend the study procedures and tolerance of wearing the sensor and transmitter continuously. Subjects continue their current MDI + FGM/CGM therapy during the run-in phase.

- Site staff will:
 - Train the subject on Blinded CGM usage (sensor insertion, transmitter use)
 - Advise subject to perform at least 4 fingerstick BG measurements per day with the study meter
 - Provide Blinded CGM Diary to Subject and instruct subject on diary completion
 - Instruct Subject to complete HFS questionnaire
 - Instruct Subject to complete DTSQs (status version of DTSQ) questionnaire
 - Instruct Subject to complete DQoL

If Visit 2 is conducted remotely, Questionnaires HFS, DTSQs and DQoL and Blinded CGM Diary will be sent to subject prior to the visit. Subject will ship them back to the site upon completion.

- Report any Adverse Events or Device Deficiency, if applicable
- Site staff will dispense supplies* to subject if visit is onsite, or ship the supplies to the subject prior to Visit 2 if the visit is conducted remotely.
 - 1 CONTOUR NEXT LINK 2.4 meter by Ascensia – *Subject will use this meter throughout the study*
 - 80 Strips (*indicative quantity for 3 weeks*)
 - 2 Guardian Link 3 Transmitters (1 is back-up),
 - 1 One-Press Serter
 - 1 Charger
 - 4 sensors (2 are back-up)
- Plan next call at Visit 3 with subject in 1 week and Visit 4 in 2 weeks.

** Note: All supplies quantities are indicative based on visit schedule and can be adjusted based on subject specific needs.*

Visit 3: Follow-Up Call [Visit 2 + 7 days (Window +3 days max)]

Site staff will call the subject to:

- Discuss sensor tolerance of subject since Visit 2
- Confirm that new sensor with same transmitter is started adequately with correct sensor insertion. Retrain subject if needed.
- Remind subject to perform at least 4 fingerstick blood glucose measurements per day with the study meter.
- Ask if any adverse event or device deficiency occurred.
- Confirm with subject next scheduled visit in 1 week (Visit 4).
- Remind subject to bring or ship back all devices and unused consumables upon blinded CGM completion for the next scheduled visit.

Visit 4*: End Run-In & Randomization [Visit 2 + 14 days (Window +7 days max)]

**Note: Visit 4 and Visit 5A can be combined to start pump therapy.*

This visit can be done remotely or onsite.

- If the Visit 4 is conducted remotely, subject will return the devices via post-mail/courier, using the provided shipping box prior to the visit.
- Site staff will collect /receive from the subject:
 - 1 Blinded CGM Diary
 - 1 CONTOUR NEXT LINK 2.4 meter by Ascensia
 - 2 Guardian Link 3 Transmitters
 - 1 Charger
 - One-Press Serter
 - Unused sensors, if applicable.

And, if visit 2 was conducted remotely:

- HFS questionnaire
- DTSQs questionnaire
- DQoL questionnaire

- Site staff will upload data from the Meter in CareLink™ Personal For Clinical Research using correct Subject ID (327-XXX-XXX).
- Site staff will upload data of Transmitter using the Download utility. Make sure to use correct file name (Subject ID_VISIT4_DATE). Refer to Blinded CGM Instructions for more details.
- Site staff will record average number of scans and % of sensor readings for FGM users and % of use of CGM for CGM users over the previous 2 weeks (based on downloaded and printed report). If the visit is conducted remotely, the site can contact the subject and record the data in medical chart or the subject can share the report via email.
- In case Blinded CGM data collection is less than 14 days (i.e. Sensor fell off), subject may be asked to repeat Blinded CGM and postpone Visit 4. Site can provide or ship new supplies to subject as needed to repeat the recording.
- Site staff will report any Adverse Events or Device Deficiency, if applicable
- Investigator will review randomization criteria per section 8.5.

If subject is eligible: subject will be randomized after completion of the Visit 4 eCRF to one of the 2 arms:

For the patients on MDI+FGM at baseline, a subject can be randomized into:

- Treatment arm: Start AHCL (and stop FGM at visit 6A)
- Control arm: Continue MDI + FGM

For the patients on MDI+ RT-CGM at baseline, a subject can be randomized into:

- Treatment Arm: Start AHCL (and stop RT-CGM at visit 6A)
- Control arm: Continue MDI + RT-CGM

- **For subject randomized to the Treatment Arm:**

Site staff will program AHCL insulin pump training.
Visit 4 and Visit 5A can be combined to start pump therapy.

- **For All Subjects:**

Site staff plans the visits with subject until Visit 9.
It is strongly recommended to schedule all study visits and calls (Visit 5 to Visit 13) with the subject, following protocol visit schedule and visit windows.

If subject is not eligible: subject will be withdrawn from the study.

All devices and unused consumables will have to be returned to the site.

For patients randomized to Treatment arm for which Visit 5A is planned to be conducted remotely, site staff will ship supplies to subject:

- 1 AHCL insulin pump
- 250 Strips
- 10 Infusion sets (1 box of 10)
- 10 Reservoirs (1 box of 10)
- 8 AA batteries (2 packs of 4)

